5.4.3.4. Sensitivity analyses

- In case the COVID-19 pandemic is still ongoing during the study conduct, the following sensitivity analyses might be considered.
 - During the assessment of long-term persistence of the immune response, the models described in Section 5.4.3.3 might be fitted taking into account participants who received the first dose of study vaccine and with full follow-up (attending all study visits).
 - Similarly, a mixed model might be fitted for the evaluation of GMT/GMC based on participants with full follow-up (attending all study visits).

The goal of this sensitivity analysis is to determine the extent to which results might be impacted by considering the different scenarios.

5.4.4. Safety analysis

Primary vaccination and revaccination dose:

The safety analysis will be performed on the ES. A descriptive analysis by group, for the 3 groups pooled up to Month 12, for the RSV_flexible revaccination and RSV_1dose groups pooled vs RSV_annual group for Month 13, Month 18 and Month 24, and by group from Month 25 up to study end, will present a summary of:

- The number and percentage of participants with at least one administration site event (solicited and unsolicited), with at least one systemic event (solicited and unsolicited) and with any AE during the 4-day or 30-day follow-up period will be tabulated with exact 95% CI after each dose. The same computations will be done for Grade 3 AEs, and for Grade 3 non-serious AEs and for AEs resulting in medically attended visit.
- The number and percentage of participants reporting each individual solicited administration site event (any grade, Grade 3 and resulting in medically attended visit) and solicited systemic event (any grade, Grade 3 and resulting in medically attended visit) during the 4-day follow-up period (i.e., on the day of vaccination and 3 subsequent days) will be tabulated for each group after each dose.
- For fever, the number and percentage of participants reporting fever by half degree (°C) cumulative increments during the 4-day follow-up period (i.e., on the day of vaccination and 3 subsequent days) will be tabulated for each group after each dose.
- The incidence of each solicited administration site event and solicited systemic event (any grade and grade 3) will be represented graphically after each dose.

- The number and percentage of participants with any unsolicited AEs during the 30day follow-up period (i.e., on the day of vaccination and 29 subsequent days) with its exact 95% CI will be tabulated for each dose by group and by Medical Dictionary for Regulatory Activities (MedDRA) Primary System Organ Class (SOC), High Level Term (HLT) and preferred term (PT). Similar tabulation will be done for Grade 3 unsolicited AEs, for any causally related unsolicited AEs, for Grade 3 causally related unsolicited AEs and for unsolicited AEs resulting in a medically attended visit. The verbatim reports of unsolicited AEs will be reviewed by a qualified person and the signs and symptoms will be coded according to the MedDRA Dictionary for Adverse Reaction Terminology. Every verbatim term will be matched with the appropriate Preferred Term.
- The number and percentage of participants with at least one report of SAE classified by the MedDRA Primary SOC, HLT and PTs and reported from Dose 1 up to 6 months post-Dose 1 and from revaccination dose up to 6 months post-revaccination will be tabulated with exact 95% CI. The same tabulation will be presented for causally related SAEs and fatal SAEs,.
- The number and percentage of participants with at least one report of causally related SAEs classified by the MedDRA Primary SOC, HLT and PTs will be reported after each dose and from Day 1 up to study end with exact 95% CI. The same tabulation will be presented for fatal SAEs.
- All SAEs will also be described in detail in a tabular listing.
- All AEs/SAEs leading to study/intervention discontinuation from dose 1 up to study end will be tabulated.
- The number and percentage of participants with at least one report of pIMD classified by the MedDRA Primary SOC, HLT and PTs and reported from Dose 1 up to 6 months post-Dose 1 and from revaccination dose up to 6 months post-revaccination will be tabulated with exact 95% CI. The same tabulation will be presented for causally related pIMDs
- The number and percentage of participants with at least one causally related pIMD classified by the MedDRA Primary SOC, HLT and PTs will be reported after each dose and from Day 1 up to study end with exact 95% CI.
- All pIMDs will also be described in detail in a tabular listing.
- The analyses of unsolicited AEs will include SAEs (unless otherwise specified).

The analysis of safety will also be performed by age category (age at Dose $1: \ge 65$ YOA, ≥ 70 YOA, ≥ 80 YOA, 60-69 YOA and 70-79 YOA) and region (North America, Europe, Asia).

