- **Study visits should preferably be done on site. As of Protocol Amendment 1 implementation, if deemed necessary, local regulations allow, and quality of study procedures is maintained, study visits during the follow-up phases can be done at home or at the LTCF, as per local regulation. Home visits are not allowed for the CMI subset (due to sensitivity of CMI samples), except in special circumstances and with the approval of the GSK Central study team. For participants without blood sample collections (i.e., for participants only being followed up for safety), contact should be attempted only if site visit is not possible at Months 6, 18, 30 and 36. For contacts, multiple formats can be proposed by the study site. These contacts may be done via email, text message, or phone call for example. The most appropriate format should be agreed between site staff and the study participant. Messaging services and email may be used as a screening to check if the participant has anything to report. If the participant answers "Yes" for at least one of the items of interest, then a phone call must be done to get the details on the event(s). Receipt of the message must be confirmed by the participant or caregiver, as applicable.
- ¹ Freely given and written informed consent must be obtained from each study participant prior to participation in the study. The participant's informed consent may be obtained prior to Visit 1.
- ² Any vaccination administered up to 1 year before administration of the first dose of study vaccine should be recorded in the eCRF. Administration of *Shingrix* at any timepoint (even if longer than 1 year before the first study dose) should be recorded in the eCRF.
- ³ Blood samples for humoral immunity (HI) and for CMI will be taken from the same ~345 participants. The remaining ~645 participants will have no blood draws. Refer to Section 6.3.4 for details.
- ⁴ Recording of any SAE or any pIMD should only be done in the 6-month post-vaccination period, i.e., from Day 1 to Month 6, from Month 12 to Month 18, and from Month 24 to Month 30.
- ⁵ SAEs related to study participation, or to a concurrent GSK medication/vaccine should be collected from the time of consent obtained (prior to administration of Dose 1) up to study end.
- 6 Blood sampling should be performed prior to vaccination (this has been clarified for the vaccination visit occurring after implementation of Protocol Amendment 1).

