- **Study visits should preferably be done on site. **As of Protocol Amendment 1 implementation,** if deemed necessary, **local regulations allow, and quality of study procedures is maintained,** study visits during the follow-up phases for the humoral subset can be done at home or at the LTCF, as per local regulation. **Home visits are not allowed for the CMI subset** (due to sensitivity of CMI samples) except in special circumstances and with the approval of the GSK Central study team.
- ¹ Freely given and written informed consent must be obtained from each study participant prior to participation in the study. The participant's informed consent may be obtained prior to Visit 1.
- ² Any vaccination administered up to 1 year before administration of the first dose of study vaccine should be recorded in the eCRF. Administration of *Shingrix* at any timepoint (even if longer than 1 year before the first study dose) should be recorded in the eCRF.
- ³ Blood samples for humoral immunity will be taken from all participants. Refer to Section 6.3.4 for details.
- ⁴ CMI blood samples should only be taken from ~115 participants. Refer to Section 6.3.4 for details.
- ⁵ Recording of any SAE or any pIMD should only be done in the 6-month post-vaccination period, i.e., from Day 1 to Month 6 and from Month 24 to Month 30.
- ⁶ SAEs related to study participation, or to a concurrent GSK medication/vaccine should be collected from the time of consent obtained (prior to administration of Dose 1) up to study end.
- ⁷ Blood sampling should be performed prior to vaccination (this has been clarified for the revaccination visit occurring after implementation of Protocol Amendment 1).
- ⁸ Visits at Month 30 must not be performed before the 6-month post-vaccination timepoint to allow collection of safety data up to at least 6 months after each vaccination for each participant (this has been clarified for the revaccination visit occurring after implementation of Protocol Amendment 1).

^{*}Refer to Table 7 for the description of study groups.

Table 3 Schedule of activities: RSV_1dose* (Amended: 01 April 2022)

Type (V = visit)**	٧	V	V	V	V	V	٧	V	N. C.
Timepoint	D1	D31	M6	M12	M18	M24	M30	M36	Notes
Study participant informed consent ¹	•								See Section 10.1.3 for details
Check with participant if he/she will appoint a caregiver and distribute caregiver information letter, when applicable	0	0	0	0	0	0	0	0	See Section 5.2.5 for details

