- ² Any vaccination administered up to 1 year before administration of the first dose of study vaccine should be recorded in the eCRF. Administration of *Shingrix* at any timepoint (even if longer than 1 year before the first study dose) should be recorded in the eCRF.
- ³ Blood samples for humoral immunity will be taken from all participants. Refer to Section 6.3.4 for details.
- ⁴ CMI blood samples should only be taken from ~115 participants. Refer to Section 6.3.4 for details.
- ⁵ Recording of any SAE or any pIMD should only be done from Day 1 to Month 6.
- ⁶ SAEs related to study participation, or to a concurrent GSK medication/vaccine should be collected from the time of consent obtained (prior to administration of Dose 1) up to study end.

Table 4 Intervals between study visits for group RSV_annual

Interval	Length of interval	Allowed interval
Day 1 → Day 31	30 days	30-42 days
Day 1 → Month 6	180 days	180-210 ¹ days
Day 1 → Month 12	365 days	350-380 days
Month 12 → Month 13	30 days	30-42 days
Month 12 → Month 18	180 days	180-210 ¹ days
Day 1 → Month 24	730 days	715-745 days
Month 24 → Month 25	30 days	30-42 days
Month 24 → Month 30	180 days	180-210 ¹ days
Day 1 → Month 36	1095 days	1080-1110 days

¹ Visit must not be performed before the 6-month post-vaccination timepoint to allow collection of safety data up to at least 6 months post-vaccination for each participant.

For the intervals, exclusion from the per-protocol set will be defined in the Statistical Analysis Plan (SAP).

Table 5 Intervals between study visits for groups RSV_flexible revaccination and RSV_1dose (Amended: 01 April 2022)

Interval	Length of interval	Allowed interval
Day 1 → Day 31	30 days	30-42 days
Day 1 → Month 6	180 days	180-210 ¹ days
Day 1 → Month 12	365 days	350-380 days
Month 12 → Month 18	180 days	180-210 days
Day 1 → Month 24	730 days	715-745 days
Month 24 → Month 25 ²	30 days	30-42 days
Month 24 → Month 30	180 days	180-210 ¹ days
Day 1 → Month 36	1095 days	1080-1110 days

¹ Visit must not be performed before the 6-month post-vaccination timepoint to allow collection of safety data up to at least 6 months post-vaccination for each participant. *Note that the 6-month safety follow-up following revaccination at Month 24 is only applicable for the RSV flexible revaccination group.*

For the intervals, exclusion from the per-protocol set will be defined in the SAP.

² Only applicable for the RSV_flexible revaccination group.

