Study Groups	Number of participants	Age	Primary vaccination	Revaccination Year 1 (Month 12)	Revaccination Year 2 (Month 24)	Open
RSV_annual*	~990	≥60 years	RSVPreF3 OA investigational vaccine	RSVPreF3 OA investigational vaccine	RSVPreF3 OA investigational vaccine	х
RSV_flexible revaccination	~330	≥60 years	RSVPreF3 OA investigational vaccine	(none)	RSVPreF3 OA investigational vaccine	х
RSV_1dose	~330	≥60 years	RSVPreF3 OA investigational vaccine	(none)	(none)	х

* RSV_annual group will be split in 3 technical groups in SBIR in order to have a randomization ratio of 1:1:1:1:1: for treatment allocation and avoid predictability.

• **Groups and sub-groups definition for analysis:** Refer to the tables below for a description of the groups and subgroups labels that will be used in the Tables Figures and Listings (TFLs).

The analyses pertaining to timepoints up to Month 12 will be performed for each group and for the 3 groups pooled. From Month 13 up to study end, the analyses will be performed by group.

The following group names will be used in the TFLs:

Table 2 Group names and definition for footnote in the TFLs

Group order in tables	Group label in tables	Group definition for footnote	
1	RSV_annual	Participants receiving the first dose (Dose 1) of RSVPreF3 OA investigational vaccine at Day 1, followed by a revaccination dose at 12 months post-Dose 1 and at 24 months post-Dose 1	
2	RSV_flexible revaccination	Participants receiving the first dose (Dose 1) of RSVPreF3 OA investigational vaccine at Day 1 and a revaccination dose at 24 months post-Dose 1	
3	RSV_1dose	Participants receiving a single dose (Dose 1) of RSVPreF3 OA investigational vaccine at Day 1	

Pooled Group label in tables	Groups to be pooled	Pooled definition for footnote	Comment
Total	RSV_annual, RSV_flexible revaccination and RSV_1dose	Participants receiving one dose of RSVPreF3 OA investigational vaccine at Day 1 in all the three groups	Applicable on data reported up to Month 12
Flexible+1dose	RSV_flexible revaccination, and RSV_1dose	Participants receiving one dose of RSVPreF3 OA investigational vaccine at Day 1 in the RSV_flexible revaccination, and RSV_1dose groups	Applicable on data reported at Month 13, Month 18 and Month 24

Table 3Pooled group names and definition for footnote in the TFLs

Table 4Sub-group names and definitions for footnote in the TFLs

Sub-analysis	Subgroup order in tables	Subgroup label in tables	Subgroup definition for footnote

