5.1.3. Reactogenicity/Safety

- For a given participant and the analysis of solicited events within 4 days postvaccination, missing or non-evaluable measurements will not be replaced. Therefore, the analysis of solicited events will include only vaccinated participants with documented solicited safety data (i.e., paper diary completed).
- For analysis of unsolicited AEs, serious adverse events (SAEs), potential immunemediated diseases (pIMDs) and concomitant medications, all vaccinated participants will be considered. Participants who did not report an event or concomitant medication will be considered as participants without the event or the concomitant medication, respectively.

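### SAP 5.4.4 sets undosed groups beside dosed groups for adverse-event classes collected only after a dose, and SAP 5.1.3 then counts uncollected events as absent

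*SAP*

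**What the plan says.** **Layout.** SAP Amendment 3, Section 5.4.4, orders a descriptive safety summary with RSV_flexible revaccination and RSV_1dose "groups pooled vs RSV_annual group for Month 13, Month 18 and Month 24", then by group from Month 25 to study end. SAP Section 3.1, Table 3, defines a matching Flexible+1dose column: "Applicable on data reported at Month 13, Month 18 and Month 24". The items listed include any AE, solicited events, unsolicited AEs, SAEs and pIMDs. Protocol Section 9.4.4.3 has the same layout for Months 13 and 18.

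**Collection.** Protocol Section 1.3 limits all-SAE and all-pIMD recording separately for each group:
- RSV_annual (Table 1, footnote 4): "from Day 1 to Month 6, from Month 12 to Month 18, and from Month 24 to Month 30".
- RSV_flexible revaccination (Table 2, footnote 5): "Recording of any SAE or any pIMD should only be done in the 6-month post-vaccination period", which for this group means Day 1 to Month 6 and Month 24 to Month 30.
- RSV_1dose (Table 3, footnote 5): "Recording of any SAE or any pIMD should only be done from Day 1 to Month 6".

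The notes to Protocol Table 14 (Section 8.3.1) tie solicited events, unsolicited AEs and all SAEs/pIMDs to a preceding vaccination. Protocol Section 10.3.8.1 collects fatal SAEs, related SAEs, related pIMDs and AEs/SAEs leading to withdrawal in every group to study end. It does the same for SAEs linked to study participation or to a concurrent GSK product.

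**Counting.** For unsolicited AEs, SAEs and pIMDs, SAP Section 5.1.3 considers all vaccinated participants and adds: "Participants who did not report an event or concomitant medication will be considered as participants without the event or the concomitant medication, respectively". Solicited events are treated differently: "the analysis of solicited events will include only vaccinated participants with documented solicited safety data".

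**The concern.** Each rule is reasonable alone; together they conflict. The layout asks for a column for groups that had no dose in the window. The protocol does not seek most of the listed events in those groups then. The counting rule turns the absence of a report into the absence of an event.

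RSV_flexible revaccination (until Month 24) and RSV_1dose are the only randomised, concurrent groups without revaccination. A table that sets their uncollected events beside the fully collected events of RSV_annual would make ordinary background SAEs, pIMDs and AEs look like an excess after revaccination. SAP Section 7.1 marks the Month 13 and end-of-study analyses for public posting as well as for the study report, so such a table could reach readers who do not know the collection schedule.

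**Working it through.** **Step 1: the plan's own safety figure.** Protocol Table 23 gives the chance of seeing at least one AE, 1 − (1 − p)^N. At p = 0.5%:
- N = 990: 1 − 0.995^990 = 99.30% (plan: 99.3%)
- N = 330: 1 − 0.995^330 = 80.87% (plan: 80.9%)

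Both reproduce and are not in dispute. They also show that the plan sizes revaccination safety on 990 and 330, with no reduction for dropout.

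**Step 2: where all-SAE/pIMD collection differs.** From the three schedule tables:

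| Window | RSV_annual | RSV_flexible | RSV_1dose | Equal? |
|---|---|---|---|---|
| Day 1 to M6 | yes | yes | yes | yes |
| M6 to M12 | no | no | no | yes |
| M12 to M18 | yes | no | no | **no** |
| M18 to M24 | no | no | no | yes |
| M24 to M30 | yes | yes | no | **no** |
| M30 to M36 | no | no | no | yes |

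Unsolicited AEs follow the same pattern, but only for 30 days after each dose.

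**Step 3: what the undosed column would show if the SAP is followed literally.**
- *Solicited events:* no diary, so N = 0. No percentage is produced.
- *Non-serious unsolicited AEs:* about zero. An AE leading to withdrawal could still appear.
- *All SAEs and all pIMDs:* an undercount. Only fatal, related, withdrawal-leading or participation-related events can appear.

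The pooled column has 330 + 330 = 660 participants. For zero events the exact 95% upper limit is 1 − 0.025^(1/n):
- n = 660: 0.56%
- n = 330 (RSV_1dose alone, Months 24-30): 1.11%

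Those limits would look precise about events that nobody sought.

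**Step 4: illustration of size.** The documents give no background rates, so every rate here is an assumption, taken as equal in both columns. For the undosed groups I further assume that 0 to 20% of SAEs fall in a class that is still collected. Expected count = N × rate; displayed count = 660 × rate × (0 to 0.20).

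| Assumed 6-month SAE rate | RSV_annual, of 990 | Pooled, true, of 660 | Pooled, displayed |
|---|---|---|---|
| 1% | 10 | 7 | 0-1 |
| 2% | 20 | 13 | 0-3 |
| 4% | 40 | 26 | 0-5 |
| 6% | 59 | 40 | 0-8 |

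For unsolicited AEs at an assumed 30-day rate of 5 to 20%, RSV_annual would show 50 to 198 of 990. The pooled column would show about 0 of 660 where 33 to 132 would be expected.

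**Step 5: classes collected everywhere.** SAP Section 10.1.1 attributes an event to the most recent dose. A fatal SAE at Month 14 therefore belongs to the Month 12 dose in RSV_annual but to Dose 1 in the other two groups. Even these classes can be compared only over a window defined by calendar time since Dose 1.

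**The case against.** The strongest reply is that the individual tables are anchored to doses. In SAP Section 5.4.4 the AE tables are per dose, and the all-SAE and all-pIMD tables run for six months from Dose 1 or from the revaccination dose. SAP Section 5.4.5 adds a 30-day table after each vaccination. A participant with no revaccination date has no such window, so undosed groups might simply have no column. On that view, vaccinated in Section 5.1.3 means given the dose in question. The tables that run to study end cover related SAEs, fatal SAEs, related pIMDs and events leading to discontinuation, which are largely the classes collected in all groups. The trial has no control and all analyses are descriptive, and the table shells, which would settle the layout, are not among the documents.

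Much of this stands: it shows that the misleading table is one reading of the SAP and not its certain output. It does not remove the conflict. The opening sentence of the same section prescribes the pooled comparison at Months 13 and 18, when the pooled groups have had no second dose. The safety set is everyone with at least one dose (SAP Section 4.1). SAP Section 5.4.6 plans a full-follow-up sensitivity analysis if more than 10% miss revaccination or lack safety data after it, which suggests that participants without the dose stay in the main denominators. No sentence marks undosed groups as not applicable. A descriptive percentage still has to be correct.

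**Conclusion.** The point holds in a limited form. The SAP's layout and counting rules, read literally, misreport events that were not collected. This affects Months 12-18 for both undosed groups and Months 24-30 for RSV_1dose. Non-serious unsolicited AEs would appear as about 0/660 (0 to 0.56%) after Month 12, all-SAE and all-pIMD cells would be too low, and solicited events would have no denominator.

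A reader might infer three stronger things that the documents do not support:
- *That the undosed groups would show no SAEs or pIMDs by construction.* Fatal, related, withdrawal-leading and participation-related events are still collected there, so the cells are undercounts and not certain zeros.
- *That the whole of Months 13-24 is affected.* RSV_annual also stops all-SAE and all-pIMD recording from Month 18 to Month 24.
- *That the spurious excess can be quantified,* for example as 2 to 6 percentage points on 792 revaccinated participants. No background SAE rate is given. The 792 (990 × 0.8) borrows the 20% yearly non-evaluable allowance, which the plan does not apply to its safety sizing.

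The collection windows and the SAP rules are taken from the documents. The 0/660 interval also assumes full planned enrolment and the literal reading. The illustrative counts rest on assumed rates.

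**What to change.** In SAP Sections 5.4.4 and 5.1.3:
1. Limit post-revaccination tables of solicited events, unsolicited AEs, all SAEs and all pIMDs to participants who received that dose. Where an undosed group appears in the layout, print *not collected*.
2. Exempt those cells from the rule that no report means no event.
3. After Month 6, compare groups only on classes collected in all of them: fatal SAEs, related SAEs, related pIMDs, and AEs/SAEs leading to withdrawal. Use a common calendar window from Dose 1, not the most recent dose.

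The cost is SAP wording and table shells. No protocol change and no extra data collection in RSV_1dose is needed.

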10.3.8.1. Time period for collecting and recording AEs, SAEs and pIMDs

All solicited administration site and systemic events that occur during 4 days following administration of each dose of study vaccine must be recorded into the appropriate section of the eCRF, irrespective of intensity. All unsolicited AEs that occur during 30 days following administration of each dose of study vaccine must be recorded into the appropriate section of the eCRF, irrespective of intensity or whether or not they are considered vaccination-related.

The time period for collecting and recording SAEs and pIMDs will begin at the first receipt of study vaccine and will end 6 months after study vaccine administration.

All SAEs and pIMDs considered related to study vaccination, any fatal SAEs and AEs/SAEs leading to withdrawal from the study will be collected and recorded from the time of the first receipt of study vaccine until the participant is discharged from the study. SAEs related to study participation or to a concurrent GSK medication/vaccine will be collected from the time consent is obtained until the participant is discharged from the study.

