8. CHANGES TO THE PROTOCOL DEFINED STATISTICAL ANALYSIS

This statistical analysis plan complements the analyses described in the protocol.

The changes compared to the planned statistical analysis specified in the Protocol amendment 1 (Dated: 01 April 2022) are described below:

• The number and percentage of participants with at least one administration site event (solicited only), with at least one systemic event (solicited only) and with any solicited event during the 4-day follow-up period after vaccination

- Related SAEs/pIMDs and Fatal SAEs will be tabulated after each dose.
- SAEs/pIMDs within 30 days following each vaccination.

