10.1.1. Attributing events to vaccine doses

The dose relative to an event is the most recent study dose given to a participant prior to the start of a given event. For example, if the start date of an AE is between Dose 1 and Dose 2, the relative dose will be Dose 1.

If an event starts on the same day as a study dose, the relative dose will be derived from the additional information provided in the case report form (CRF) using the contents of the flag indicating if the event occurred before or after study dose. If 'after vaccination is selected, the relative dose for the event will be the one administered on the start day of the event. If 'before vaccination is selected, the relative dose for the event will be the dose prior to this one.

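### At end of study, the open-ended per-dose tables of fatal SAEs, related SAEs and related pIMDs set post-Dose 1 periods of about 12, 24 and 36 months side by side

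*SAP*

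**What the plan says.** SAP Amendment 3, section 5.4.4, gives two layers of tables for the same three event types.

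- **Six-month tables.** After the table of all SAEs up to 6 months after Dose 1 and after revaccination: "The same tabulation will be presented for causally related SAEs and fatal SAEs". After the matching pIMD table: "The same tabulation will be presented for causally related pIMDs".
- **Tables with no stated limit.** The number and percentage with a related SAE "will be reported after each dose and from Day 1 up to study end with exact 95% CI". For deaths: "The same tabulation will be presented for fatal SAEs". Related pIMDs get the same sentence as related SAEs.

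Section 8 lists the second layer as a departure from the protocol: "Related SAEs/pIMDs and Fatal SAEs will be tabulated after each dose". Protocol 9.4.4.3 had asked for these events only over the whole study period.

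The end of a post-dose period follows from other parts of the plan:

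- SAP 10.1.1: "The dose relative to an event is the most recent study dose given to a participant prior to the start of a given event".
- Protocol 10.3.8.1: related SAEs and pIMDs and fatal SAEs "will be collected and recorded from the time of the first receipt of study vaccine until the participant is discharged from the study".
- SAP 3.1, Table 2: RSV_annual receives Dose 1 "followed by a revaccination dose at 12 months post-Dose 1 and at 24 months post-Dose 1". RSV_flexible has one further dose, at 24 months, and RSV_1dose has none. Follow-up is about 36 months for everyone.

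Under SAP 5.1.3 all vaccinated participants count in the analysis of SAEs and pIMDs. No person-time is planned.

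**The concern.** Elsewhere in 5.4.4 and 5.4.5 a per-dose table carries its window: 4 days, 30 days or 6 months. Here none is given. Reading it as 6 months would make it repeat the tables already ordered for the same events, so taken literally it is a further, open-ended table. In such a table a Dose 1 event counts until the next dose or the end of follow-up, and that time differs by design between the groups.

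A crude percentage grows with time at risk, and an exact binomial interval does not correct for that. Deaths in adults aged 60 and over accrue with time whatever the vaccine does. The post-Dose 1 row would therefore tend to show the fewest deaths in RSV_annual and the most in RSV_1dose even if risk were identical. Within RSV_flexible, Dose 1 would be observed for twice as long as Dose 2. SAP 7.1 sends the end-of-study analysis to public posting and the study report.

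**Working it through.** **The plan's own figure.** The documents give no number for these tables. The only safety calculation is Protocol Table 23, the chance of at least one event, 1 − (1 − p)^n. At p = 0.5% it gives 0.9930 for n = 990 and 0.8087 for n = 330, matching the stated 99.3% and 80.9%.

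**Windows at end of study (nominal).**

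| Row | RSV_annual | RSV_flexible | RSV_1dose |
|---|---|---|---|
| Post-Dose 1 | Day 1 to Month 12: 365 days | Day 1 to Month 24: 730 days | Day 1 to Month 36: 1095 days |
| Post-Dose 2 | Month 12 to 24 | Month 24 to 36 | none |
| Post-Dose 3 | Month 24 to 36 | none | none |

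The post-Dose 1 ratios to RSV_annual are 730/365 = 2.0 and 1095/365 = 3.0. With the intervals allowed in SAP Table 6 (350–380, 715–745 and 1080–1110 days) they range over 715/380 = 1.88 to 745/350 = 2.13, and 1080/380 = 2.84 to 1110/350 = 3.17. The other rows are about 12 months each.

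**Equal constant hazard, complete follow-up.** The event rate is an assumption, taken here as 0.1% to 3% a year. With yearly risk r, the expected percentage over t years is 1 − (1 − r)^t.

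| r per year | RSV_annual (t = 1) | RSV_flexible (t = 2) | RSV_1dose (t = 3) | Ratios |
|---|---|---|---|---|
| 0.1% | 0.10% | 0.20% | 0.30% | 2.00, 3.00 |
| 1% | 1.00% | 1.99% | 2.97% | 1.99, 2.97 |
| 3% | 3.00% | 5.91% | 8.73% | 1.97, 2.91 |

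At 1% the expected participants with events are 990 × 1.00% = 9.9, 330 × 1.99% = 6.6 and 330 × 2.97% = 9.8. Exact 95% intervals would be 0.5–1.8% for 10 of 990 and 1.5–5.5% for 10 of 330.

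**What shrinks the ratios (r = 1%).**

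- *Loss to follow-up of 20% a year.* This borrows the non-evaluable rate in Protocol 9.2 as a high value for loss of safety follow-up. With h = −ln 0.99 and d = −ln 0.80, the percentage is h/(h + d) × [1 − exp(−(h + d)t)], giving 0.90%, 1.61% and 2.17%. Ratios: 1.79 and 2.42.
- *Missed doses, participants staying in follow-up.* If 10% receive none of their planned revaccinations, RSV_annual shows 0.01 + 0.1 × 0.99 × 0.0199 = 1.20%, RSV_flexible 0.0199 + 0.1 × 0.9801 × 0.01 = 2.09% and RSV_1dose 2.97%. Ratios: 1.74 and 2.48. If instead the Month 12 and Month 24 doses were each missed by 10% independently, RSV_annual would show 0.01 + 0.1 × 0.99 × 0.01 + 0.01 × 0.9801 × 0.01 = 1.11%, with ratios of about 1.9 and 2.7.
- *Risk clustered after the dose.* If a share c of the three-year risk falls soon after Dose 1, the percentage is proportional to c + (1 − c)t/3. For c = 0.5 the ratios are 1.25 and 1.5; for c = 0.8, 1.08 and 1.15; for c = 1, both are 1.

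**The fixed-window tables.** At 1% a year in every group and complete follow-up, the 6-month post-Dose 1 table shows 0.50% in all three, and Day 1 to Month 36 shows 2.97% in all three.

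**The case against.** The strongest reply is that valid comparisons are already planned beside these rows. The 6-month tables cover the same events over equal periods, and the sentence that orders the per-dose table also orders Day 1 to study end, where nominal follow-up is equal. That stands, and it limits the fault to one set of tables.

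Several other replies carry weight:

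- The unlimited window is inferred from 5.4.4 and 10.1.1 together; no sentence says it outright. The inference is sound, because the 6-month reading would duplicate other output, but the gap could be closed by wording alone.
- Only post-Dose 1 rows are affected. Up to Month 12 the windows are equal. At Months 18 and 25 the gap is opening, but SAP 7.1 marks those analyses as internal. The full contrast belongs to the end-of-study analysis.
- Missed revaccinations lengthen the RSV_annual window and so narrow the difference.
- The group footnotes in SAP Table 2 give each schedule, so an attentive reader can work out the periods. They do not state the window for the row.

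That all analyses are descriptive (SAP section 6) means no test is falsified. It does not help the reader of the table, for whom the percentage and its interval are the result.

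A reader might infer that the plan would make annual revaccination appear to lower mortality. The documents do not support that. The RSV_annual post-Dose 1 row stops at revaccination, so it says nothing about events afterwards, and the Day 1 to study end percentage from the same tabulation would show no difference under equal risk.

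**Conclusion.** The point holds for the end-of-study post-Dose 1 rows. As written, they put crude percentages over about 12, 24 and 36 months side by side, and those percentages are not comparable between groups. Post-Dose 2 and post-Dose 3 rows are not materially affected.

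It would be tempting to say that equal risk will look like a two- to three-fold difference. Those are ceilings: they need a constant hazard, complete follow-up and every planned dose given. A constant hazard is most reasonable for deaths. For related SAEs and related pIMDs the risk may cluster after dosing, and the distortion could then be small. The direction and the window lengths come from the documents; the event rates, attrition and clustering are assumptions.

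It would also be wrong to say that the trial lacks a valid between-group comparison of these events. Two are already in section 5.4.4.

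**What to change.** In SAP 5.4.4 and section 8, state the period for the open-ended per-dose tables of fatal SAEs, related SAEs and related pIMDs, in one of two ways:

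- report events per person-year, with time counted from the dose to the next dose, withdrawal, death or study end, and an exact Poisson 95% CI; or
- cap the tables at a common 12 months post-dose (or the next dose, if it falls slightly earlier).

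Under an equal constant risk of 1% a year, the first gives −ln 0.99 = 0.01005, about 10 per 1,000 person-years in every group, and the second gives 1.00% in every group. The cap is the safer choice for related events: if their risk clusters after dosing, a person-year rate is diluted in the groups with longer windows.

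With either choice, footnote the window by group. Leave the 6-month and the Day 1 to study end tables as they are. A 6-month cap would only repeat existing output.

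The cost is SAP wording, one exposure-time derivation from dates already collected, and extra columns in a few tables. No new data and no change to study conduct are needed.
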